There are several major limitations in the discussed prior studies that support the *scientific premise* for this proposal. The first major limitation is the use of BMI to estimate offspring adiposity during infancy and childhood. BMI in adults is related to clinical outcomes, however the predictive value and usefulness in infants, children, and adolescents is less clear⁹³. The use of BMI in infants, children, and adolescents is further complicated by the inter-individual variability among children for periods of rapid growth for which BMI cannot distinguish changes in FM or lean mass. In infants and children, there is a twofold range of variation in fatness for a given BMI value⁹⁴. However, in studies using sophisticated methods to directly assess offspring body composition and AT distribution, relationships between maternal DHA and offspring body composition are supported⁷².

Another limitation is that information or variability on maternal pre-pregnancy BMI and GWG are limited or lacking in the Muhlhausler⁸⁹ and Hauner⁸⁰ et al. studies. The Muhlhauser⁸⁹ study has a mean maternal pre-BMI of 26 kg/m² with a range that had few obese women (23.2-30.5 kg/m²) and GWG was not collected and not included in the analysis. The sample from the Hauner et al. study was even leaner (22.3±3.0 kg/m²) and GWG was ~15.5±5.0 kg with no report on percentage excessive GWG. The ADORE cohort from which we will recruit in Kansas City so far has a mean pre-pregnancy BMI of 28.5±7.1 kg/m² with a wide pre-pregnancy BMI range (17.4-50.1 kg/m²). GWG data are not yet available in the ADORE cohort, however, in [name] prior DHA study (KUDOS) in Kansas City, the mean GWG was 16.4±7.1 kg with GWG classification of 62% excessive. Our study will provide important data from a representative cohort to understand when controlling for excess maternal weight and excess GWG, what effect DHA has on offspring body composition.

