be requested upon Release of Information form expiration. Medical records are reviewed for adverse events upon receipt and all adverse events are recorded by body system and coded by diagnosis within body system. For each adverse event, the following information is recorded: diagnosis, body system code for the diagnosis, whether the event was a serious adverse event, event start date, event ongoing dates if applicable, event stop date, treatment including names of medications, age of child in mos at the start of the event, and location of service for the event (ex. Hospital, pediatric clinic, urgent care clinic). Records are coded by one individual and then checked for accuracy by a second person.

D5i) Air Displacement Plethysmography to measure total fat mass and fat-free mass: Pea Pod (COSMED) will be used as an additional method to measure body composition at 2 weeks and 6 months. The Pea Pod assesses body volume and density to calculate fat mass and fat-free mass. The test will be conducted according to manufacturer guidelines.

D5j) Steps to maximize retention: At KUMC, we use the ClinCard system, which works like a debit/credit card. At study enrollment, subjects are given a card that looks like a debit/credit card with a number unique to each participant. At the completion of study visits with incentives, staff log in and the card is loaded with the respective stipend amount within 24-48 hours. The card can be used anywhere Visa/Mastercard is accepted. For each study visit completed, subjects will be paid \$125 (total \$500 if all visits are completed). If a DXA scan is unable to be acquired during any study visit, subjects may be asked to return at a later date and will receive an additional \$50 for returning. Please refer to **Table 5** for the incentive schedule.

The *scientific rigor* of this application is high. We are following a cohort born to women participating in an already NIH funded and approved RCT that has been vetted for safety and efficacy which provides strength to this proposal. For the outcomes of this proposal, we are using DXA to assess body composition and distribution which is the only precise technique for evaluating amount and location of body fat.

Table 6. Research timeline and activities.							
Research Activities	2017	2018	2019	2020	2021	2022	2023
icocaren netivities							
Hiring/train personnel	—						
Develop data collection	_						
protocols							
IRB submission	—						

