Recruitment/screening							
Data collection							
Data collection							
Data entry							
Data collection ends							
Data analysis and							
writing							
Manuscript prep &							
submission							

D6) **Study timeline**: Listed in **Table 6** is the timeline for the study.

D7): **Statistical analyses**: The primary purpose of this study is to determine if there are differences in the offspring FM at 24 months when exposed prenatally to high vs. low DHA supplementation and if maternal GWG status impacts this relationship (appropriate or excessive GWG).

D7a) **Aim 1 analysis:** Using a two-way analysis of variance (ANOVA) on the 24 months FM, we will test for a statistical interaction between GWG group and DHA dose. The specific interaction from this ANOVA will test the contrast to **investigate if the supplement of 1000 mg DHA/day compared to 200 mg DHA/day during pregnancy can reduce infant FM at 24 months and specifically if this reduction is greater in offspring exposed to excessive GWG versus appropriate GWG.** A two sided t-test statistic (alpha=0.05) is calculated from the appropriate contrast from the two-way ANOVA (GWG and DHA).

D7b) **Aim 2 analysis:** A three-way analysis of variance (ANOVA) on the 2 year central FM, we will test for a statistical interaction between both GWG and DHA dose and offspring gender and DHA dose.

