D7c) **Longitudinal analysis:** Additionally, we will perform a linear mixed model to explore differences between the high vs. low supplement groups for infant FM and distribution. The dependent variable will be infant FM or infant central FM and the independent variable will be DHA group (fixed effect) and time (4 visits: 2 wks, and 6, 12, and 24 months). The model will include the fixed effects of treatment, time and the treatment-time interaction, with the subject effect treated as random to account for the dependence among repeated observations. This analysis allows for unbalanced data (allows for missing data). We will use exploratory analyses to investigate, in a univariate fashion, covariates. GWG and infant gender will be included as well as other potential covariates including parity, maternal age, pre-pregnancy BMI, parity, education level, maternal diet, infant diet, infant age at test, gestational age at birth, and socioeconomic status. An auto-regressive covariance structure will account for unevenly spaced visits. For missing outcome data, the data vector will be used to impute the missing value. Infant gender will be explored both as a confounder and as an effect modifier to account for differences in growth rates. We will analyze the data without confounding variables and repeat the analysis with confounding variables.

D7d) **Power calculation:** We performed a power analysis based on pilot data reported in **Table 2**. We calculated a total of n=120 would be required to answer the primary aim. Of the total n=120, we anticipate n=54 will experience appropriate GWG (45%) and n=66 will experience excessive GWG (55%) with each approximately equally allocated to low and high DHA supplementation groups. For the given effect size (population mean differences of -168 vs 304 grams), the power is 0.815. This means that 81.5% of studies would be expected to yield a significant effect to detect an interaction, rejecting the null hypothesis that the two population means are equal. The test is two-sided. Allowing for 33% attrition, this increases the sample size to n=180. To answer the primary aim in a second group of Spanish speaking subjects, we will increase the sample size by n=180 for a total sample of n=360.

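### The primary DHA x GWG test on 24-month fat mass is valid but unadjusted; a pre-specified ANCOVA on infant sex, age at scan and pre-pregnancy BMI could gain precision at little cost

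*Combined protocol and SAP*

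**What the plan says.** D7a (Aim 1 analysis) sets the primary test as "Using a two-way analysis of variance (ANOVA) on the 24 months FM". The two-sided t statistic at alpha 0.05 "is calculated from the appropriate contrast from the two-way ANOVA (GWG and DHA"). No covariate is named.

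D7b (Aim 2 analysis) brings infant sex into its model, but for central fat mass: "we will test for a statistical interaction between both GWG and DHA dose and offspring gender and DHA dose".

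D7c (Longitudinal analysis) is an additional mixed model. Its stated terms are: "The model will include the fixed effects of treatment, time and the treatment-time interaction". On covariates it says: "GWG and infant gender will be included as well as other potential covariates including parity, maternal age, pre-pregnancy BMI"; age at test is further down the same list. Covariates are to be explored one at a time. The section closes: "We will analyze the data without confounding variables and repeat the analysis with confounding variables".

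Three other places bear on the point:
- The discussion of prior studies' limitations (end of A9) says the study will show, "when controlling for excess maternal weight and excess GWG, what effect DHA has on offspring body composition".
- D2 reports that the pilot interaction came from an ANCOVA that included pre-pregnancy BMI, infant gender and age at test.
- D5j allows for a delayed scan: "If a DXA scan is unable to be acquired during any study visit, subjects may be asked to return at a later date". The summary of protocol changes also reports a longer visit window. Age at the 24-month scan can therefore vary.

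**The concern.** An interaction contrast adds the sampling error of four cell means, so it needs precision more than a main effect does. Variation in 24-month fat mass due to sex, age at scan or maternal BMI goes into the error term of D7a, although the study will hold all three variables. A9 describes maternal BMI as related to offspring fat mass, and D7c cites sex differences in growth rates.

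D7c does not fill the gap. Its model names no DHA x GWG term and its covariate set is not fixed. Its closing sentence does not say whether it reaches Aim 1. If an adjusted Aim 1 result is intended, its covariates could be chosen after the data are seen.

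There is also a question of interpretation. A3 says that overweight and obese women more often gain excessively, and A9 links BMI to offspring fat mass. A reader of a positive DHA x GWG result will ask whether BMI lies behind it.

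**Working it through.** **Inputs from the documents**
- D7d: n=120 evaluable, 54 with appropriate and 66 with excessive GWG, each split about equally by dose. Cells are 27, 27, 33 and 33.
- D7d: written effect of -168 vs 304 g; stated power 0.815.
- Table 2, change in fat mass from birth to 3 months (g): low DHA 1189.5 (SD 549.9) with appropriate and 1499.0 (622.4) with excessive GWG; high DHA 1330.4 (640.7) and 1026.4 (539.3).
- D7d adds a second group of 180, so n=240 evaluable if the language groups are pooled (cells 54, 54, 66, 66).

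**Assumed:** the covariate R2 within cells (5 to 30%), and that the 3-month Pea Pod SD can stand in for the SD of 24-month DXA fat mass. The documents give neither.

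**Formulas**
- SD = root mean square of the four Table 2 SDs = 589.7, about 590 g.
- SE = SD x sqrt(1 - R2) x sqrt(sum of 1/n per cell). At n=120 the last factor is sqrt(2/27 + 2/33) = 0.367.
- Power from the noncentral t, two-sided 0.05, df = n - 4 - (number of covariates).

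**The plan's own figure first.** Table 2 gives DHA differences (low minus high) of 1189.5 - 1330.4 = -140.9 g and 1499.0 - 1026.4 = 472.6 g. The interaction contrast is 472.6 + 140.9 = 613.5 g. Unadjusted SE is 590 x 0.367 = 216.5 g, the ratio is 2.83 and power is 0.80, close to 0.815. Read literally, D7d's effect is 304 + 168 = 472 g, which gives a ratio of 2.18 and power 0.58. An SD of about 447 g would be needed to reach 0.815, below every fat-mass SD in Table 2. The written values match 1330.4 - 1499.0 and 1330.4 - 1026.4, which are not the two DHA differences. That mismatch is a separate issue; both readings are carried below.

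**Closed-form power**

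| Contrast, n | Unadjusted | R2 5% | 10% | 20% | 30% |
|---|---|---|---|---|---|
| 613.5 g, 120 (3 covariates) | 0.80 | 0.82 | 0.84 | 0.88 | 0.92 |
| 613.5 g, 240 (4 covariates) | 0.979 | 0.984 | 0.988 | 0.994 | 0.998 |
| 472 g, 120 (3 covariates) | 0.58 | 0.60 | 0.63 | 0.68 | 0.73 |

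The SE falls by 1 - sqrt(1 - R2), which is 3, 5, 11 and 16%.

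**Cost of adjustment.** The closed form ignores chance imbalance in the covariates. Allowing for it, the expected variance rises by a factor of 115/112 at n=120 with three covariates, so break-even R2 = 1 - 112/115 = 2.6%. With four covariates it is 1 - 111/115 = 3.5%. At n=240 with four covariates it is 1 - 231/235 = 1.7%.

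**Simulation at n=120** (4000 trials per setting, SD 590 g), unadjusted vs adjusted power:

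| R2 | 613.5 g, 4 covariates | 472 g, 3 covariates |
|---|---|---|
| 0 | 0.82 vs 0.80 | 0.573 vs 0.561 |
| 5% | 0.80 vs 0.81 | 0.583 vs 0.585 |
| 10% | 0.80 vs 0.83 | 0.576 vs 0.611 |
| 20% | 0.80 vs 0.87 | 0.581 vs 0.660 |
| 30% | 0.80 vs 0.92 | 0.582 vs 0.723 |

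With no interaction, the three-covariate simulation rejected in 4.4 to 5.5% of trials for both models.

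**The case against.** The strongest reply is that nothing is wrong with D7a. It fixes outcome, time point, contrast, alpha and sidedness, and its type I error is sound. There is no covariate set to choose in the primary test, so any freedom of choice affects only a supplementary adjusted analysis. All of this stands.

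The size of the benefit is also uncertain. The documents say that BMI is related to offspring fat mass but not how strongly, and they quantify no sex or age effect on total fat mass. D5b takes GWG from self-reported pre-pregnancy weight; if BMI rests on the same report, it may predict less well. At R2 of 5% and n=120 the simulated gain is one point or less. If the groups are pooled and the contrast is 613.5 g, power is already 0.979. This stands too, and is why the benefit is stated as possible.

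D7c's closing sentence may have been meant to cover Aim 1. Even so, it would name neither the covariates nor the primary result.

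Two stronger readings are tempting. A reader might infer that the plan contradicts itself, because A9 speaks of controlling for maternal weight. That sentence is rationale for the study as a whole, and D7c does list BMI. A reader might also infer that omitting BMI invalidates the primary test. DHA dose is randomized, the null rejection rate is unaffected, and the documents report no DHA x BMI effect.

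**Conclusion.** The point holds as an efficiency recommendation. D7a's test is valid; a pre-specified ANCOVA could sharpen it using data already collected or planned. At n=120 with the Table 2 contrast, simulated gains are about 3 to 12 points of power for R2 between 10 and 30%, against a loss of 1 to 2 points if the covariates explain nothing. These figures rest on the assumed R2, on 590 g as a stand-in SD and on D7d's cell sizes.

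A reader might take the 0.58 as showing that the design depends on covariates to be viable. It does not: that figure comes from D7d's written effect, while the contrast in Table 2 gives 0.80 without adjustment.

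The BMI question concerns how a positive result would be read, not its error rate. A BMI main effect would not rule out a DHA x BMI effect appearing as DHA x GWG.

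**What to change.** In D7a:
- Take the same DHA x GWG contrast from an ANCOVA with infant sex, pre-pregnancy BMI and age at DXA, plus language if the two language groups are pooled.
- State in advance whether age is chronological or corrected. This matters because the parent trial tests whether DHA changes early preterm birth.
- Fix the set before treatment codes are linked to the 24-month fat-mass data.
- Keep the unadjusted two-way ANOVA as a sensitivity analysis.
- Say whether D7c's closing sentence applies to Aim 1.

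A companion model that adds DHA x pre-pregnancy BMI is optional. It should be labelled an aid to interpretation that covers one possible modifier and corrects no error rate.

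The cost is analysis-plan wording and 3 of 116 residual degrees of freedom at n=120, or 4 with language. No new data are needed.

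### The Aim 1 ANOVA has no rule for children without a 24-month fat mass value, and the mixed model that keeps their earlier scans has no DHA x GWG term to answer Aim 1

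*Combined protocol and SAP*

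**What the plan says.** - **Primary analysis (D7a).** The method is given as "Using a two-way analysis of variance (ANOVA) on the 24 months FM", and the effect of interest is the DHA-by-GWG interaction. The test is specified ("A two sided t-test statistic (alpha=0.05) is calculated from the appropriate contrast"), but nothing is said about children whose 24-month fat mass (FM) is missing.
- **Attrition (D7d).** The primary aim needs 120 children. "Allowing for 33% attrition, this increases the sample size to n=180", and a second group of the same size brings the total to 360.
- **Mixed model (D7c).** This additional, exploratory model uses the 2-week, 6-, 12- and 24-month visits and is described as tolerating missing data. "The model will include the fixed effects of treatment, time and the treatment-time interaction". On GWG it says only: "GWG and infant gender will be included as well as other potential covariates". The one effect modifier named is sex: "Infant gender will be explored both as a confounder and as an effect modifier". The covariance is a random subject effect with an auto-regressive structure.
- **Imputation (D7c).** One sentence says that a missing outcome will be filled in from the data vector. It gives no method and does not mention D7a.
- **Earlier data.** Table 5 schedules DXA at all four visits. D3 lets a family enter at any of them, including 24 months.

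**The concern.** Aim 1 asks whether the DHA effect on 24-month FM differs between excessive and appropriate GWG. The analysis that tests this ignores the scans at 2 weeks, 6 and 12 months. The analysis that uses those scans compares DHA groups averaged over GWG, so it does not address Aim 1.

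Two things are at stake. The first is precision: a child scanned at 12 months but not at 24 adds nothing to the primary contrast. The second is robustness: if children with more or less fat at earlier visits are more likely to be lost, and this differs between the four DHA-by-GWG cells, the contrast among children measured at 24 months is shifted. Enlarging the sample for attrition protects power but does not remove such a shift.

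The imputation sentence adds a further uncertainty. If it were applied to the ANOVA with an imputation model lacking DHA x GWG, the imputed values would be pulled towards no interaction.

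**Working it through.** **1. The plan's own figure.** 120 / (1 - 0.33) = 179.1, taken up to 180, so D7d reproduces. The allowance covers 180 - 120 = 60 children per 180, or about 120 of 360.

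Other figures in D8 bracket it. Past retention of 80-88% means 12-20% lost to follow-up. Multiplying by scan success at its stated floor of 75% gives 0.80 x 0.75 = 0.60 and 0.88 x 0.75 = 0.66, so 34-40% without a scan. That assumes the two are independent and no repeat scan succeeds.

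**2. Can D7c give the Aim 1 contrast?** The contrast at 24 months is (low minus high DHA, excessive GWG) minus (low minus high DHA, appropriate GWG). With visit as a category it needs GWG x DHA and GWG x DHA x time. With only DHA, time, DHA x time and a GWG covariate, the fitted DHA difference at 24 months is the same in both GWG groups, so the contrast is zero by construction.

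**3. Precision gained from earlier scans.** Let obs be the fraction with a 24-month value (0.67, from D7d), rec the fraction with an earlier scan only, and rho the correlation of earlier with 24-month FM. The documents give neither rec nor rho, so both are assumed. Relative to observed cases only:

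variance ratio = (1 - rho²) + rho² x obs / (obs + rec)

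| rho | rec | Calculation | Variance ratio | SE ratio |
|---|---|---|---|---|
| 0.5 | 0.10 | 0.75 + 0.25 x 0.67/0.77 | 0.97 | 0.98 |
| 0.7 | 0.20 | 0.51 + 0.49 x 0.67/0.87 | 0.89 | 0.94 |
| 0.8 | 0.20 | 0.36 + 0.64 x 0.67/0.87 | 0.85 | 0.92 |

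If every lost child had an earlier scan (one third lost), the ratio becomes 1 - rho²/3. The 120 completers would then count as 120 / (1 - rho²/3): 124, 131, 143, 153 and 164 for rho of 0.3, 0.5, 0.7, 0.8 and 0.9. These are upper bounds.

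**4. Robustness.** Simulation with one earlier scan and these inputs:

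- SD 590 g, pooled from the four FM-change cells of Table 2: √[(549.9² + 640.7² + 622.4² + 539.3²)/4] = 589.7. These are 3-month changes, used only for scale.
- About one third missing, rho 0.5-0.9, and log-odds of loss rising by 0.5-1.0 per SD of earlier FM (assumed).
- The D7d interaction: 304 - (-168) = 472 g.

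| Where loss depends on earlier FM | True interaction | Error, observed cases only |
|---|---|---|
| Excessive-GWG, low-DHA cell only | 0 | about -44 to -147 g |
| All four cells alike | 0 | about 0 |
| All four cells alike, earlier scans carrying the full cell effect | 472 g | about -12 to -65 g |

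A likelihood-type estimate that uses the earlier scan within each cell was within about 3 g of the truth throughout. These are scenarios, not forecasts.

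**The case against.** Several points on the other side stand.

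- **The plan never says that children are dropped.** It follows from running an ANOVA on 24-month FM without a missing-data rule. A broad reading of the D7c imputation sentence could feed imputed values into D7a. The sentence sits in the longitudinal section, however, and names no method.
- **The 33% is a planning allowance.** A reader might infer that a third of children will contribute nothing. The documents do not forecast that: D8 reports 80-88% retention, D5a and D8 allow repeat scans (at most 8 in total), and D5j pays for return visits. The allowance is already in the sample size, so there is no shortfall from planned numbers.
- **Entry can be late.** Children first seen at 24 months are fully used by the ANOVA. Those lost before any scan cannot be recovered by any model.
- **Bias largely cancels in the interaction if loss works alike in all four cells.** With no true effect the error is about zero; with a true effect it is attenuation. The larger errors need loss that differs between cells. No passage suggests this, and C1c keeps participants and staff blind to capsule assignment.
- **The mixed model does not repair everything.** If a toddler cannot be scanned because of their state at 24 months, and that state is related to FM beyond what earlier scans show, the mixed model is biased too.
- **D7c was offered as exploratory.** An ANOVA at the primary time point matches Aim 1 and the test that was powered, so replacing it is a preference rather than a necessity.

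None of this supplies D7a with a missing-data rule or D7c with a GWG interaction. GWG might be said to be included in D7c, but it is listed with the covariates, and only sex is named as a modifier.

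**Conclusion.** The point holds as a gap in specification and a missed use of scheduled data. D7a is an observed-case analysis by default, the imputation sentence is undefined and unattached to it, and the model suited to incomplete follow-up cannot produce the Aim 1 contrast.

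The precision gain is modest and depends on the assumed correlation and the assumed share of children with an earlier scan only. Protection against loss related to earlier FM matters chiefly if that relation differs between the four cells.

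A stronger conclusion, that the planned ANOVA is biased or that the mixed model would cure selective scan failure, is not supported. The documents do not say how loss relates to FM. The change is worth making because it costs little, not because the primary result is shown to be wrong.

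**What to change.** 1. In D7c, add GWG, GWG x DHA, GWG x time and GWG x DHA x time. Treat visit as a category, and use an unstructured within-child covariance in place of the random subject effect with auto-regressive structure.
2. Report the GWG x DHA contrast at 24 months from this model for Aim 1. Preferably make it the primary estimate, with the two-way ANOVA on observed values as sensitivity. At the least, prespecify it as a sensitivity analysis beside the ANOVA.
3. In D7a, state how children without a 24-month value are handled. In D7c, name the imputation method and the analyses it serves, or delete the sentence. Require any imputation model to contain the DHA x GWG interaction.

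The cost is plan wording and a few model terms, on scans already scheduled. The downside is a slightly more complex model: four visits give 4 x 5 / 2 = 10 covariance parameters.
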